## 5. Study design and methods

Study Overview: Patients with major depression diagnosed based on DSM-V TR criteria between the ages of 18 and 65 (males, females and minorities) will be recruited to ensure a range of inflammation from low to high (as determined by plasma CRP). Research assessments will occur in the clinical research space of the Principal Investigator in the Emory Clinic Buildings and at the Emory University School of Medicine EUH CRN, a dedicated clinical research unit in the Emory University Hospital. Following a minimum of 2 screening visits to determine study eligibility (see inclusion and exclusion criteria below) and stability of plasma CRP concentrations (or at PI's, study physician or their designee's discretion), patients will undergo psychiatric assessments and ratings and will have a medical history and physical examination along with laboratory testing and research blood draw, and will undergo weight, height, waist circumference, body composition measurements, and a urine drug screen followed by behavioral testing. Patients may also be asked to undergo finger prick at screening or study visits to collect 20 ul of blood that will be used to rapidly measure CRP on a Diazyme hsCRP POC Test Kit (or equivalent as approved by PI or PI's designee) without patients having to undergo venipuncture. Patients may also be asked to have a lumbar puncture (LP) performed by an Emory Anesthesiologist on a separate visit between 7am-12 pm following hydration with 1 L of saline IV using standard sterile technique and local anesthesia with patients in the lateral decubitus position. Approximately 11 cc of CSF will be withdrawn. Upon completion of the LP, subjects will lie flat for approximately one hour and be subsequently discharged after ~4-6 hours from admission. Patients will participate in two additional outpatient study visits (see Table 1 for study protocol). The LP visit may occur approximately 1 week either before the first neuroimaging Study visit or one week after the last neuroimaging Study Visit, unless otherwise approved by the PI. After subjects have completed screening by meeting inclusion/exclusion criteria and moved into the L.P. and/or scanning visit phase of the study, an Abbreviated Clinical Interview and depression self-report (PHQ-9, see below) will be conducted if it has been more than 2 weeks since psychiatric assessments. Additional laboratory and medical assessments will be conducted if more than 4 weeks from screening, unless otherwise approved by the PI, study physician or PI's designee. This information will be used as study data and/or to improve patient safety by enabling monitoring of a subject's physical and psychiatric status during the study. Drastic fluctuations in psychiatric status (i.e. >25% change in depression scores) or medically significant changes in health status from H&P or labs will trigger a review by the Study Team (including the PI and/or study physicians) to evaluate appropriateness for continuation in the study and/or consider referral for further

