
treatment. Additional CRP testing, psychiatric assessments, or medical assessments may be conducted as indicated by the PI, study physician or PI's designee. Prior to each MRI neuroimaging session, patients will undergo a urine toxicology screening (Testcup for drugs of abuse, or equivalent as approved by PI or PI's designee) for safety and exclusion of substance abuse. On the last screening visit, patients will undergo blood sampling in the morning (collected at the same time as blood draw for safety labs and/or CRP), and complete neurocognitive testing. During Study Visits 1 & 2, subjects will complete a series of self-reports in the morning, have MRI scans (including resting-state fMRI and ASL) pre- and post-L-DOPA or placebo administration from about 9 AM to 12:30 PM, and undergo blood sampling and selected neurocognitive testing after the MRI scans from about 12:30 to 2 PM. L-DOPA or placebo, which will be administered double-blind (randomized by the Emory IDS), will be administered in the waiting area of the Neuroimaging Facilities. Patient's vital signs will be monitored by a Study Physician or designated Nurse Practitioner before, during, and after drug administration. At each study visit, 6 ml of research blood will be collected at 4 degree for extraction of plasma to measure inflammatory markers and/or L-DOPA concentrations. Two 3 ml samples will be collected (at the screening visit #2 only) for whole blood mRNA gene expression. 2 buffy coat samples from the first research blood collected for plasma (screening visit #2) will also be stored for genetic analyses of relevant gene polymorphisms and DNA methylation. In order to further assess immune cell profiles, we will also collect 10 ml of whole blood in EDTA at room temperature for immune cell extraction. Some samples may be sent to other labs for additional analysis. Safety laboratory tests will be conducted at screening, which will include a hematocrit (CBC with automated differential), electrolyte panel (comprehensive metabolic panel), urinalysis with microscopic, and serum quantitative pregnancy test (for women only). A CRP test will be completed at both screening visits to establish stability, and may be repeated during study visits at the PI's or PI's designee's discretion. Subjects who smoke cigarettes must refrain from smoking 30 minutes before all blood draws and 2 hours prior to mRNA sampling. Subjects who smoke half a pack per day, or e-cigarette equivalent, will be offered a nicotine patch during study visits to reduce the effects of withdrawal on fMRI scans.

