  - h) urinalysis with microscopic
  - i) serum quantitative pregnancy test (if female)
  - j) urine toxicology for drugs of abuse
  - k) Pt/INR (only done if S will be participating in the LP procedure)
  - l) PTT (only done if S will be participating in the LP procedure)

Procedures	Initial Visit	Screening #1†	Screening #2†	Lumbar Puncture Visit	Additional (If needed)	Study Visits #1-3
Consent/re-consent	X	[X]	[X]	[X]	[X]	[X]

Physical exam		X	[X]		[X]	[X]
Health update and vitals			[X]	[X]		[X]
Concomitant Medications		X	X	X	[X]	X
Adverse Events		X	X	X	[X]	X
History of Chronic Conditions		X			[X]	
CRP	[X]	X	[X]	[X]	[X]	[X]
Safety Labs #	[X]	X	[X]	[X]	[X]	[X]
Additional Safety Labs ##	[X]	[X]	[X]	[X]	[X]	[X]
Pt/INR, PTT (for LP only)	[X]	[X]	[X]	[X]	[X]	[X]
Research blood draws †		[X]	X	[X]	[X]	X
MRI Scan						X
Neurocognitive tests		[X]	X	[X]	[X]	
Neurocognitive tests *				[X]		X
Psychiatric Assessments Y	X	[X]	[X]	[X]	[X]	[X]
Psychiatric Assessments YY		X	[X]	[X]	[X]	
Psychiatric Assessments YY Y				[X]		X
Self Reports	X	[X]				
Self Reports *			X	[X]	[X]	
Self Reports **						X
MRI Scan Food, Drink and Cigarette Intake Form +						X
Lumbar Puncture				X		
Placement of ECG patches		[X]	[X]		[X]	

[X]: To be completed when indicated.

† Screening 1 & 2 can be completed on the same day if preferred by patient

#Safety Labs: Complete Metabolic Panel, CBC w diff, Serum Preg Test (females), Urinalysis w micro, Urine drug test

##Additional Safety Labs (screening #1 or screening #2): HIV Ag/Ab, Hep B Ag, Hep C Ab, ANA, TSH, Glycosylated Hemoglobin, EKG, Chem 7: electrolytes, urea, creatine, glucose, and/or hsCRP

Pt/INR, PTT to be completed for subjects who consent to LP within 2 weeks of procedure at any visit

‡ To be completed at one of the two screening visits during collection of safety labs and/or screening CRP

Neurocognitive tests: EEFRT, TMT-A, TMT-B, Digit Symbol Task, FTT, Reaction Time Task, Choice Reaction, Delayed Matching to Sample, Spatial Working Memory, RAVLT, Stroop word and color test to be completed at the end of the last screening visit

Neurocognitive tests\* (Visits 1 & 2): EEFRT, TMT-A, Digit Symbol Task, FTT, Reaction Time Task

Y Psychiatric Assessments (Initial Visit): PHQ-9 or QIDS

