**Baseline Assessments:** During screening, a research blood sample (18 ml total) may be collected along with blood draw for safety labs and/or CRP measurement. Research blood will be used for measurement of plasma inflammatory markers, mRNA gene expression for inflammatory signaling pathways, circulating and mRNA gene expression markers related to metabolism and endocrine hormones, and buffy coat to examine polymorphisms in relevant inflammatory proteins. For female subjects, questions pertaining to menopausal status will also be obtained using a Staging System for Reproductive Aging questionnaire. All patients will also complete a Composite Vascular Risk Profile Scale. A complete series of neurocognitive testing may also be performed during the last screening visit or the LP visit. The baseline research blood and neurocognitive assessments are necessary to complete prior to randomization to study treatment. They may be collected along with screening assessments that are being conducted to determine eligibility for the LP procedure or randomization to study drug, or at the LP visit. Physiological measures including heart rate and activity may also be recorded using adhesive ECG patches. These data may also be used independently of qualification for further study participation. To reduce patient burden, a 15 minute break will be given in between motivational and motor assessments. Participants will receive \$25 for this visit, an additional \$25 if research blood is collected, and an additional \$25 if ECG patches are placed. Patients will also receive \$50 for completing motor and motivational assessments, and up to \$60 for completing the EEfRT based upon the subject's responses.

**ECG patches for collection of biometric data (optional):** Patients will be given the option of wearing ECG patches (MC10 BioStamp®) to record physiological measures including heart rate and activity. Trained members of the study team will place the ECG patches on the chest of the subject and they will record heart rate and activity over 24 hours. Another patch may need to be placed on the subject's leg; the subject will be trained to do this themselves. These patches will be returned to the study team either at the next study visit or by a pre-paid envelope that will be provided to the subject.

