**Analytic Strategy, Objective 2:** Similar to the analytic strategy for Objective 1, post-L-DOPA or placebo administration neurocognitive performance or self-report scores will be entered into linear models with CRP (or other inflammatory markers) while controlling for pre-administration behavioral scores as well as relevant covariates. The difference (delta; post minus pre) in behavioral scores before and after placebo and L-DOPA will also be compared by paired T test, and between patients with high and low inflammation (CRP > or < 3mg/L). L-DOPA-related changes in functional connectivity in Objective 1 will then be compared to relevant post-LDOPA task-based and self-report behavioral responses using linear modeling.

**Analytic Strategy, Objective 3:** Relationships between functional connectivity and behavior before and after L-DOPA with central and peripheral inflammatory cytokines and their soluble receptors, and biomarkers of their potential effects on dopamine through decrease BH4 activity will be explored. Gene transcripts associated with inflammatory and metabolic signaling pathways related to inflammation effects on the brain have been used to predict response to pharmacological therapies (54, 95), including our previous work (96, 97). Therefore, genome-wide gene expression will be assayed. Plasma and CSF will be collected on a separate visit to measure IL-6, IL-1 $\beta$ , TNF and their soluble receptors, CSF BH4, dopamine, HVA and DOPAC, and plasma phenylalanine and tyrosine. Linear regression will be used to examine relationships between functional connectivity Z-scores or behavior (dependent variables) and biomarkers of inflammation and dopamine synthesis (independent variables), while controlling for covariates. Cytokines and their receptors will be examined first independently (with and without correction for multiple comparisons), then together in models to identify biomarker(s) that are most significant after backward and forward linear regression. If variables are collinear (as assessed by variance inflation factor, tolerance and leverage plots), principal component analysis (PCA) will be used.(98) Gene expression that correlates with CRP, or differs between patients with

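### The Objective 3 plan collects its plasma predictors with CSF at what reads as the optional lumbar puncture visit, in conflict with the pre-randomization research plasma planned elsewhere

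*Combined protocol and SAP*

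**What the plan says.** **Objective 3 analysis plan (Section 7, Analytic Strategy, Objective 3).** The collection rule is "Plasma and CSF will be collected on a separate visit to measure IL-6", with IL-1β, TNF and the soluble receptors, and then "CSF BH4, dopamine, HVA and DOPAC, and plasma phenylalanine and tyrosine". Linear regression relates connectivity or behaviour to these markers. No analysis set or sample size is given.

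**The LP visit (Section 5, Study Overview).** "Patients may also be asked to have a lumbar puncture (LP) performed by an Emory Anesthesiologist on a separate visit". On timing: "The LP visit may occur approximately 1 week either before the first neuroimaging Study visit or one week after the last neuroimaging Study Visit". The screening laboratory list marks the clotting tests as "only done if S will be participating in the LP procedure". Expected uptake is not stated.

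**Blood outside the LP visit (Section 5).**
- The Study Overview has blood sampling at the last screening visit and takes buffy coat from "the first research blood collected for plasma (screening visit #2", so research plasma is drawn there.
- The schedule table shows research blood as a firm entry at Screening #2 and as a bracketed, when-indicated entry at the LP visit.
- The Baseline Assessments paragraph says "Research blood will be used for measurement of plasma inflammatory markers" and makes baseline research blood a condition for randomization. It words the screening draw permissively and allows the LP visit as an alternative.
- The Study Overview also plans 6 ml at each study visit for inflammatory markers, L-DOPA concentrations, or both.

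**The concern.** Hypothesis 3 is about prediction: markers of inflammation and of dopamine synthesis are expected to forecast who responds to L-DOPA. A predictor needs to be measured before the response, and in as many analysed patients as possible.

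The Objective 3 collection sentence puts both at risk for the plasma markers. CSF can come only from the LP, and the Study Overview describes the LP, like the Objective 3 sentence, as a separate visit. If plasma is taken with it, patients without an LP have no Objective 3 plasma cytokine, phenylalanine or tyrosine value. Patients whose LP follows the last imaging visit have a value obtained after both dosing days.

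The peripheral half of the hypothesis would then be tested in a self-selected subset of unknown size, partly with samples taken after the outcome they are meant to predict. The protocol already plans blood that avoids both problems.

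**Working it through.** **1. Which visit is meant.** Set side by side:

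| Place | What it implies for Objective 3 plasma |
|---|---|
| Section 7, Objective 3 | Collected with CSF on a separate visit |
| Section 5, Study Overview (LP) | CSF comes from a separate, optional visit, about a week before the first or after the last imaging visit |
| Section 5, Study Overview (blood) | Research plasma drawn at screening visit #2 |
| Section 5, schedule table | Research blood firm at Screening #2, when indicated at the LP visit |
| Section 5, Baseline Assessments | Baseline research blood complete before randomization; used for plasma inflammatory markers |

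The first two rows together point to the LP visit. The last three point to a baseline sample. They cannot all describe the source of the same predictors.

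**2. Which markers are affected.**
- Phenylalanine and tyrosine: most firmly tied, because no other passage assigns them to a named draw.
- Cytokines and soluble receptors: tied by the Objective 3 sentence, but the baseline blood is also assigned to plasma inflammatory markers.
- CRP and whole-blood gene expression: not affected; both come from screening.

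**3. Timing.** The baseline blood must precede randomization. The LP-visit alternative for that blood therefore works only when the LP comes before dosing. An LP a week after the last imaging visit yields plasma taken after both study treatments. The study-visit blood is no substitute: it is drawn after the post-dose scan.

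**4. Size of the loss.** The plan gives no power figure for Objective 3. Its only power statement concerns Objective 1 (dz about 1, n=30 per group, more than 80% power). A paired t-test gives 99.96% at n=30 and 99.88% at n=27, so that statement holds as a lower bound, but it has no bearing here.

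For a single correlation at two-sided α=0.05 with 80% power, Fisher's z gives

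r_min = tanh[(1.960 + 0.842)/√(n − 3)].

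Power for an assumed true correlation of 0.30 is Φ[atanh(0.30)·√(n − 3) − 1.960], with atanh(0.30) = 0.3095. The analysable total of 80 and α are from the protocol; uptake and r=0.30 are assumptions.

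| LP uptake (assumed) | n | √(n − 3) | r_min | Power at r=0.30 |
|---|---|---|---|---|
| All 80, baseline plasma | 80 | 8.775 | 0.309 | 0.775 |
| 75% | 60 | 7.550 | 0.355 | 0.647 |
| 50% | 40 | 6.083 | 0.431 | 0.469 |
| 25% | 20 | 4.123 | 0.591 | 0.247 |

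These are single-marker figures without covariates or multiplicity adjustment. They show the direction and range of the loss, not a forecast.

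**The case against.** The strongest reply is that the plan never restricts the peripheral-marker analyses. Objective 3 defines no analysis set, and a separate visit could mean only separate from the imaging days. The LP procedure text describes CSF withdrawal and no plasma draw. Objective 1 uses the Aim 3 peripheral indices to interpret its own results, and Objective 2 allows other inflammatory markers in its models, neither with any LP condition. The study is a pilot, the Objective 3 relationships are exploratory, and no power is claimed for them.

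Much of this stands. A reader might infer that the analyses are confined to LP volunteers by design. The documents do not support that: the restriction arises only if the Objective 3 sentence is followed literally, and the baseline blood points the other way for inflammatory markers. Nor is screening plasma guaranteed for everyone, since the Baseline Assessments wording is permissive and allows the LP visit.

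A reader might also infer that plasma and CSF markers enter one selection model, which would drop every patient without CSF and come close to saturation. The plan says cytokines and receptors are examined singly, "then together in models to identify biomarker(s) that are most significant after backward and forward linear regression". It does not say that the two fluids share a model, and it provides principal components for collinear variables.

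What the reply does not remove is the collection rule itself. It groups plasma with CSF, it conflicts with three places in Section 5, and nothing says which sample prevails. For phenylalanine and tyrosine it is the only instruction.

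**Conclusion.** The conflict is real and should be resolved before samples are chosen for assay. Taken literally, the Objective 3 text limits plasma cytokines, soluble receptors, phenylalanine and tyrosine to LP volunteers and permits post-dose plasma as a predictor. The actual loss cannot be computed because uptake is not given. Over an assumed 75% down to 25% uptake, the detectable correlation rises from 0.309 to between 0.355 and 0.591: modest if most patients have the LP, substantial if few do.

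The timing problem does not depend on how many patients have an LP, only on some of them having it after dosing. The documents do not say whether these markers would still be altered a week after a single dose, so the point is one of temporal order rather than a demonstrated bias.

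**What to change.** Reconcile the Objective 3 paragraph of Section 7 with the Study Overview, the schedule table and the Baseline Assessments paragraph, and state the following:

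1. The Objective 3 plasma predictors, including phenylalanine and tyrosine, come from the pre-randomization baseline research sample. Blood drawn at an LP visit counts as baseline only if that visit preceded randomization.
2. Plasma-marker models are fitted in all analysed patients.
3. CSF-marker models are fitted in the LP subset. Report its n and how many LPs came before and after dosing.
4. LP-visit plasma is otherwise used only for same-day plasma–CSF correlations.

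The cost is plan wording and a choice of which stored sample to assay. No procedure is added, assuming the baseline plasma volume covers the extra analytes. The small downside is that, for LP patients, baseline plasma is generally not same-day with CSF; item 4 covers that need.

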
**Enrollment:** For this pilot study, we plan to enroll 225 subjects with major depression to analyze data from 80 patients. We will ensure that subjects represent a full range of inflammation from low to high. Therefore, at least one-third of subjects will have a screening plasma CRP concentration <3 mg/L, one-third of subjects will have CRP 1-3 mg/L, and one-third subjects will have CRP >3 mg/L, measured at least twice to establish stability and rule out acute infection. Patients will be obtained from multiple referral resources including the Emory Clinic, Grady Health System, the Veterans Administration Medical Center (VAMC), and community psychiatrists. Depressed subjects will also be obtained from newspaper and radio advertisements as well as internet solicitation. We anticipate that at least 4 subjects per month will consent to enter our study. This estimate is based on ongoing projects that have been recruiting subjects for related studies over the past 5 years.

**Compensation:** Participants will be compensated using ClinCard. The ClinCard is a web-based, reloadable debit card that automates reimbursements for clinical research participants. An additional \$25 will be provided to cover travel expenses for participants that travel equal to or greater than 50 miles to Atlanta.

**Initial visit/consent signing:** After signing the consent form, subjects will complete an office intake visit(s) for further evaluation. After providing written informed consent, subjects will complete the Patient Health Questionnaire (PHQ-9) or the Quick Inventory of Depressive Symptomatology Self-Report (QIDS-SR). If eligible, subjects may undergo the initial CRP test and possibly other laboratory tests. Subjects will be compensated \$25 for this initial intake visit.

**Appointment Scheduling & Reminders:** All participants will be given the opportunity to receive appointment reminders and scheduling information via text message on their mobile phones. If the subject consents to this form of communication, study staff will only use OhMD Texting Service to communicate with participants. This platform provides a Desktop and Mobile Version of OhMD for the research team to securely communicate with participants and maintain subject confidentiality. This service will only be used for communicating relevant appointment information and never used for PHI. Participants will receive the following text message

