from the study team upon first contact: "Please do NOT send any personal information via text. You may call the study team at [REDACTED] to discuss any personal or health details." Any PHI received via text message will be reported to the IRB as a potential breach of confidentiality.

Eligibility for completing further screening and baseline assessments: The PI or PI's designee will review information collected from the initial visit to determine whether subjects are eligible to proceed with further screening and collection of baseline assessments based on the following:

- (1) Attainment of informed consent
- (2) Psychiatric clinician has determined presence of current depressive symptoms at intake with QIDS score  $\geq 14$  or PHQ-9 score  $\geq 15$ , unless otherwise approved by the principal investigator or PI's designee
- (3) The patient has not informed study staff or the psychiatric clinician of any condition that, in the opinion of the PI or PI's designee, would make the patient unsuitable for or unable to complete further screening

Medical and data quality screening criteria for LP and randomization: Subjects determined to be eligible for the study will undergo a minimum of 2 screening visits. Subjects will be compensated \$50 at each screening visit. The screening visits will include the following assessments:

- (1) Structured Clinical Interview for DSM-V (SCID)
- (2) Mini Mental State Exam (MMSE), a standard, 27-item assessment of general cognitive functioning.
- (3) Childhood Trauma Questionnaire
- (4) Bipolarity Index
- (5) Scale for the Assessment of Negative Symptoms (SANS)
- (6) Salpêtrière Retardation Rating Scale (SRRS)
- (7) Wide Reading Achievement Test (WRAT-3)
- (8) Psychiatric History Form
- (9) HDRS
- (10) SHAPS-C
- (11) MGH-ATRQ (Lifetime and Current)
- (12) Medical history and physical exam performed by a physician or nurse practitioner.
- (13) CRP (This lab is collected at least twice to establish stability – the mean will be used for group assignment. A difference of greater than 50% between values or a CRP  $\geq 10$  mg/L will warrant additional CRP sampling.)
- (14) Laboratory testing including:
  - a) an electrocardiogram
  - b) complete blood count with automated differential
  - c) comprehensive metabolic panel (with renal and hepatic function tests)
  - d) antinuclear antibodies
  - e) glycosylated hemoglobin test
  - f) thyroid stimulating hormone
  - g) tests for HIV Ag/Ab, HBV Ag, and HCV Ab,

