## **Inclusion and Exclusion Criteria:**

### **Inclusion**

- informed consent has been discussed with subject, subject has been given opportunity to ask questions, and has signed a current version of the consent and HIPAA documents prior to initiation of study procedures
- age 18-65 years including males, females and minorities and able to comprehend English
- diagnosis of DSM-V major depression and currently off antidepressant medication, unless otherwise approved by the PI or PI's designee
- Depression as the primary axis I disorder
- negative pregnancy test for women of childbearing potential
- not breast feeding
- two (or more) CRP tests conducted to establish reliability

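### Two same-day CRP samples can satisfy the CRP stability rules, and the enrolment quota misprints the low-CRP third as below 3 mg/L

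*Combined protocol and SAP*

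**What the plan says.** **Timing of CRP.** In Section 5, the Study Overview states that "A CRP test will be completed at both screening visits to establish stability". The Enrollment paragraph gives the purpose: CRP is "measured at least twice to establish stability and rule out acute infection". Item 13 of the screening criteria assigns the CRP group from the mean of the values. It asks for more sampling when there is "A difference of greater than 50% between values" or when a value is 10 mg/L or more. The inclusion criterion requires only "two (or more) CRP tests conducted to establish reliability".

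The procedures table footnote then allows: "Screening 1 & 2 can be completed on the same day if preferred by patient". In that table the CRP row carries a firm X only at Screening #1. Every other visit, including Screening #2, carries the bracketed mark, which the legend explains as "X]: To be completed when indicated". The initial-visit test is also optional: "If eligible, subjects may undergo the initial CRP test and possibly other laboratory tests".

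**Quota.** The Enrollment paragraph sets thirds at below 3, 1 to 3 and above 3 mg/L. Section 6 (Participant selection), the Section 7 Power Analysis and the Objective 3 strategy all use below 1, 1 to 3 and above 3 mg/L. The Power Analysis plans about 27 patients in each group.

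**The concern.** Repeat CRP is meant to separate a patient's usual level from a passing rise. Two draws on one day share the same passing state, so their agreement mainly shows that the assay repeats itself. The rules count tests but not days, so the protocol permits what the repeat was meant to prevent.

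CRP is the moderator in this trial. The Objective 1 strategy compares patients above and below 3 mg/L and tests whether the L-DOPA effect depends on CRP. Error in the CRP value blurs that grouping. The within-patient contrast of L-DOPA with placebo does not use CRP and is not affected.

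The quota error is of a different kind: it is wrong as written. A third below 3 mg/L contains nearly all of the next third, so the Enrollment paragraph alone does not secure the group below 1 mg/L that Section 7 intends to analyse.

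**Working it through.** **1. Can a same-day pair pass?** Take values of 5.0 and 5.2 mg/L from one day. The difference is 0.2/5.0 = 4%, both are below 10, and the mean of 5.1 places the patient in the high group. Every checkable CRP rule is met with no information from a second day.

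**2. How often does the 50% check fire?** The documents give no CRP variances, so these are assumptions: log-normal CRP, assay log-SD 0.1, day-to-day log-SD 0.3 to 0.6. The plan does not say whether 50% refers to the smaller or the larger value. The thresholds on the log ratio are ln 1.5 = 0.405 or ln 2 = 0.693.

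- Same day: SD of the log ratio = √2 × 0.1 = 0.141. Then 0.405/0.141 = 2.87 gives 0.4%, and 0.693/0.141 = 4.9 gives about 0%.
- Different days, day-to-day SD 0.3: SD = √(2 × (0.09 + 0.01)) = 0.447. Then 0.693/0.447 = 1.55 gives 12%.
- Different days, day-to-day SD 0.6: SD = √(2 × (0.36 + 0.01)) = 0.860. Then 0.405/0.860 = 0.47 gives 64%.

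Adding acute rises (1% to 5% per day, three- or five-fold) moves the different-day range to 14–66%. For same-day pairs the check is effectively inactive.

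**3. Effect on the high group.** This was simulated with 1.2 million patients per setting. In the central setting 30% have a usual CRP above 3 mg/L (the Introduction says CRP is elevated in up to 40%), and the between-person log-SD is 1.1. Flagged patients get one more sample on another day, and all values are averaged. The table shows how much larger the share of the high group with usual CRP of 3 mg/L or less is when everyone has same-day values instead of different-day values.

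| Acute rises per day | Excess, percentage points |
|---|---|
| none | 3.0–4.5 |
| 1%, five-fold | 2.4–4.0 |
| 2%, three-fold | 2.8–4.0 |
| 2%, five-fold | 2.2–3.5 |
| 5%, three-fold | 2.7–3.4 |
| 5%, five-fold | 1.1–2.3 |

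- With acute rises of 1–5%, the excess is 1.1–4.0 points. In patients: 27 × 0.011 = 0.3 to 27 × 0.040 = 1.1.
- Scaled by uptake of same-day-only sampling: about 0.1–0.5 of 27 at 50%, and 0.1–0.3 at 25%.
- Wider grid (20–40% above 3 mg/L, between-person log-SD 0.9–1.3): 0.4–6.1 points, or 0.1–1.7 of 27.
- Unflagged acute rises in the high group: about 0.3 to 1.6 of 27 at full uptake with no clinical detection. With 50% uptake and half detected (× 0.25), about 0.1–0.4.

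A separate simulation counted misplacement across all three CRP groups without re-sampling (median 2 mg/L, between-person log-SD 1.0, day-to-day log-SD 0.3–0.7, assay log-SD 0.05). It put 16–33% of patients in the wrong group with same-day pairs and 12–27% with different-day pairs. The direction is the same.

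**4. The quota.** The plan's own figure reproduces: 80/3 = 26.7, rounded up to 27, and 3 × 27 = 81. With the printed cut-off, 0 patients below 1, 54 between 1 and 3, and 27 above 3 mg/L would satisfy the Enrollment paragraph.

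The expected number below 1 mg/L, if only that paragraph were followed, uses the 80 − 27 = 53 patients not above 3: 53 × P(<1)/P(≤3).

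- Central: ln median = ln 3 − 0.524 × 1.1 = 0.522. P(<1) = Φ(−0.522/1.1) = 0.318. Then 53 × 0.318/0.70 = 24.
- Low end (40% above 3, log-SD 0.9): 53 × 0.167/0.60 = 15.
- High end (20% above 3, log-SD 1.3): 53 × 0.499/0.80 = 33.

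**The case against.** The pathway is narrow. It needs a patient who chooses one screening day and has no CRP from the initial visit, the lumbar puncture visit or another day. Section 6 also allows earlier screening data from the group's other studies to be reused, which may supply an other-day value. All of this limits the number affected, but none of it is required, and uptake is unknown.

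Other safeguards remain: the 10 mg/L trigger, "Medical history and physical exam performed by a physician or nurse practitioner", blood count and urinalysis, exclusions for recent antibiotics and vaccination, discretionary extra CRP tests, and rescheduling for infection signs that appear after screening. These help against infection. They do not test stability, and a rise into the range from 3 to just under 10 mg/L passes the remaining CRP trigger.

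It can be said that a same-day pair breaks the stated purpose even though it meets the count. That is fair, and it is the defect: the purpose has no operative interval behind it.

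The effect is small, and most of the gain from the change is ordinary averaging over two days, not the catching of acute rises. This stands; the table shows the largest gains with no acute rises. After the change, about 12–28% of the high group would still be misplaced under the central assumptions with acute rises of 1–5%. Objective 1 also models CRP concentration, not only the split at 3 mg/L. Still, different-day sampling lowered misplacement in every setting tried.

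On the quota, the neighbouring thirds and Sections 6 and 7 make the intent clear. That limits the practical risk to staff who work from the Enrollment paragraph alone, but that paragraph is the operative quota.

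**Conclusion.** Both parts hold.

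The same-day gap follows from the text alone. Its size rests on assumed variances and unknown uptake: under the central assumptions it is at most about one of 27 patients in the high group, and about half a patient or less at 50% uptake. It adds modest error to the CRP grouping and leaves the main treatment contrast alone. It should be closed because closing it is cheap, not because it threatens the trial. Patients with a CRP from another day are not affected.

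The quota cut-off is an error that needs no assumptions. Followed literally, it requires no patient below 1 mg/L. In expectation it would give about 24 (range 15 to 33) instead of about 27. Sample size and power are unchanged.

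**What to change.** 1. In item 13 of the screening criteria and in the inclusion criterion, require that at least two of the CRP values used for group assignment come from different days and from the same plasma assay. Same-day screening visits can stay when a plasma CRP from the initial visit or an additional visit exists. State whether a finger-prick value counts toward classification, and whether the 50% is taken of the smaller or the larger value.
2. In the Enrollment paragraph, change the low third to below 1 mg/L, to match Sections 6 and 7.

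**Cost.** The first change needs protocol wording and one extra plasma draw for patients who choose a single screening day and have no other-day value; the initial visit already offers a slot. Re-tests will rise: under the central assumptions 20–69% of different-day pairs trigger more sampling by either rule, against 7–11% of same-day pairs (nearly all of those by the 10 mg/L rule). The second change is one character.
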